6.5.3 Follow-up for toxicities

Patients whose treatment is permanently discontinued due to a study drug related adverse event or clinically significant laboratory value, must be followed up at least once a week for 4 weeks, until resolution or stabilization of the event, whichever comes first. Appropriate clinical experts such as ophthalmologist, endocrinologist, dermatologist, psychiatrists etc. should be consulted as deemed necessary. All patients must be followed up for adverse events and serious adverse events for 30 days following the last dose of study treatment.

6.5.3.1 Follow up on potential drug-induced liver injury (DILI) cases

Participants with transaminase increase combined with total bilirubin increase may be indicative of potentially severe DILI, and should be considered as clinically important events and assessed appropriately to establish the diagnosis. The required clinical information, as detailed below, should be sought to obtain the medical diagnosis of the most likely cause of the observed laboratory abnormalities.

The threshold for potential DILI may depend on the participant's baseline AST/ALT and total bilirubin value; participants meeting any of the following criteria will require further follow-up as outlined below:

- For participants with normal ALT and AST and total bilirubin value at baseline: AST or ALT > 3.0 x ULN combined with total bilirubin > 2.0 x ULN
- For participants with elevated AST or ALT or total bilirubin value at baseline: [AST or ALT > 3.0 x baseline] OR [ALT or AST > 8.0 x ULN], whichever occurs first, combined with [total bilirubin > 2.0 x baseline AND > 2.0 x ULN]

As DILI is essentially a diagnosis of exclusion, other causes of abnormal liver tests should be considered and their role clarified before DILI is assumed as the cause of liver injury.

A detailed history, including relevant information such as review of ethanol consumption, concomitant medications, herbal remedies, supplement consumption, history of any pre-existing liver conditions or risk factors, should be collected.

Laboratory tests should include ALT, AST, total bilirubin, direct and indirect bilirubin, GGT, GLDH, prothrombin time (PT)/INR, alkaline phosphatase, albumin, and creatine kinase.

Evaluate status of liver metastasis (new or exacerbation) or vascular occlusion – e.g. using CT, MRI, or duplex sonography.

Perform relevant examinations (Ultrasound or MRI, ERCP) as appropriate, to rule out an extrahepatic cause of cholestasis. Cholestasis (is defined as an ALP elevation > 2.0 x ULN with R value < 2 in participants without bone metastasis, or elevation of the liver-specific ALP isoenzyme in participants with bone metastasis).

Note: The R value is calculated by dividing the ALT by the ALP, using multiples of the ULN for both values. It denotes whether the relative pattern of ALT and/or ALP elevation is due to cholestatic ($R \leq 2$), hepatocellular ($R \geq 5$), or mixed ($R > 2$ and < 5) liver injury. For children, there are caveats to calculating the R-ratio as normal levels of ALP are higher than in adults with standard ranges varying by developmental age. In clinical situations where it is suspected that ALP elevations are from an extrahepatic source, the GGT can be used if available. GGT

may be less specific than ALP as a marker of cholestatic injury, since GGT can also be elevated by enzyme induction or by ethanol consumption. It is more sensitive than ALP for detecting bile duct injury (livertox.nih.gov/rucam.html).

Table 6-8 Provides guidance on specific clinical and diagnostic assessments that can be performed to rule out possible alternative causes of observed LFT abnormalities.

| Disease | Assessment |
|---------------------------------|---|
| Hepatitis A, B, C, E | IgM anti-HAV; HBsAg, IgM & IgG anti-HBc, HBV DNA; anti-HCV, HCV RNA, IgM & IgG anti-HEV, HEV RNA |
| CMV, HSV, EBV infection | IgM & IgG anti-CMV, IgM & IgG anti-HSV; IgM & IgG anti-EBV |
| Autoimmune hepatitis | ANA & ASMA titers, total IgM, IgG, IgE, IgA |
| Alcoholic hepatitis | Ethanol history, GGT, MCV, CD-transferrin |
| Nonalcoholic steatohepatitis | Ultrasound or MRI |
| Hypoxic/ischemic hepatopathy | Medical history: acute or chronic CHF, hypotension, hypoxia, hepatic venous occlusion. Ultrasound or MRI. |
| Biliary tract disease | Ultrasound or MRI, ERCP as appropriate. |
| Wilson disease (if <40 yrs old) | Caeruloplasmin |
| Hemochromatosis | Ferritin, transferrin |
| Alpha-1-antitrypsin deficiency | Alpha-1-antitrypsin |

Other causes should also be considered based upon participants’ medical history (hyperthyroidism / thyrotoxic hepatitis – T3, T4, TSH; CVD / ischemic hepatitis – ECG, prior hypotensive episodes; T1D / glycogenic hepatitis).

[REDACTED]

Following appropriate causality assessments, as outlined above, the causality of the treatment is estimated as “probable” i.e. >50% likely, if it appears greater than all other possible causes of liver injury combined. The term “treatment-induced” indicates *probably caused* by the treatment, not by something else, and only such a case can be considered a DILI case and should be reported as an SAE.

All cases confirmed on repeat testing meeting the laboratory criteria defined above, with no other alternative cause for LFT abnormalities identified, should be considered as “medically significant,” and thus, meet the definition of SAE and should be reported as SAE using the term “potential treatment-induced liver injury.” All events should be followed up with the outcome clearly documented.

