10.1.2 Serious adverse events

An SAE is defined as any adverse event [appearance of (or worsening of any pre-existing)] undesirable sign(s), symptom(s) or medical condition(s) which meets any one of the following criteria:

- fatal
- life-threatening

Life-threatening in the context of a SAE refers to a reaction in which the subject was at risk of death at the time of the reaction; it does not refer to a reaction that hypothetically might have caused death if it were more severe (please refer to the ICH-E2D Guidelines).

- results in persistent or significant disability/incapacity
- constitutes a congenital anomaly/birth defect
- requires inpatient hospitalization or prolongation of existing hospitalization, unless hospitalization is for:
 - routine treatment or monitoring of the studied indication, not associated with any deterioration in condition
 - elective or pre-planned treatment for a pre-existing condition that is unrelated to the indication under study and has not worsened since signing the informed consent
 - social reasons and respite care in the absence of any deterioration in the subject's general condition
 - treatment on an emergency outpatient basis for an event not fulfilling any of the definitions of a SAE given above and not resulting in hospital admission
- is medically significant, e.g. defined as an event that jeopardizes the subject or may require medical or surgical intervention to prevent one of the outcomes listed above

Medical and scientific judgment should be exercised in deciding whether other situations should be considered serious reactions, such as important medical events that might not be immediately life threatening or result in death or hospitalization but might jeopardize the subject or might require intervention to prevent one of the other outcomes listed above. Such events should be considered as “medically significant”. Examples of such events are intensive treatment in an emergency room or at home for allergic bronchospasm, blood dyscrasias or convulsions that do not result in hospitalization or development of dependency or abuse (please refer to the ICH-E2D Guidelines).

All malignant neoplasms will be assessed as serious under “medically significant” if other seriousness criteria are not met

Any suspected transmission via a medicinal product of an infectious agent is also considered a serious adverse reaction.

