10.1.3 SAE reporting

To ensure patient safety, every SAE, regardless of suspected causality, occurring after the patient has provided informed consent and until at least 30 days after the patient has stopped study treatment must be reported to Novartis within 24 hours of learning of its occurrence.

Any additional information for the SAE including complications, progression of the initial SAE, and recurrent episodes must be reported as follow-up to the original episode within 24 hours of the investigator receiving the follow-up information. An SAE occurring at a different time interval or otherwise considered completely unrelated to a previously reported one should be reported separately as a new event.

Any SAEs experienced after the 30 day safety evaluation follow-up period should only be reported to Novartis if the investigator suspects a causal relationship to the study treatment.

Information about all SAEs is collected and recorded on the Serious Adverse Event Report Form; all applicable sections of the form must be completed in order to provide a clinically thorough report. The investigator must assess and record the relationship of each SAE to each specific study treatment (if there is more than one study treatment), complete the SAE Report Form in English, and submit the completed form within 24 hours to Novartis. Detailed instructions regarding the SAE submission process and requirements for signatures are to be found in the investigator folder provided to each site.

Each re-occurrence, complication, or progression of the original event should be reported as a follow-up to that event regardless of when it occurs. The follow-up information should describe whether the event has resolved or continues, if and how it was treated, whether the blind was broken or not, and whether the patient continued or withdrew from study participation.

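### Protocol 6.5.3.1 gives two inconsistent SAE rules for potential drug-induced liver injury: the 'only' in one can exclude a confirmed unexplained case that the other requires to be reported

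*Protocol*

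**What the plan says.** The last two paragraphs of Protocol 6.5.3.1 each say when a liver case is an SAE.

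- **Causality paragraph.** After work-up, treatment is rated the probable cause (above 50%) "if it appears greater than all other possible causes of liver injury combined". Of such cases the text says that "only such a case can be considered a DILI case and should be reported as an SAE".
- **Closing paragraph.** It covers "All cases confirmed on repeat testing meeting the laboratory criteria defined above", provided they are left "with no other alternative cause for LFT abnormalities identified". These are called medically significant, are said to meet the SAE definition, and are given their own reporting term.

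The general safety sections work differently. Section 10.1.2 lists the seriousness criteria without reference to cause; one of them is that the event "is medically significant, e.g. defined as an event that jeopardizes the subject or may require medical or surgical intervention". Section 10.1.3 then requires "every SAE, regardless of suspected causality" to reach the sponsor within 24 hours of the site learning of it. Section 10.1.1 has the investigator record relationship to treatment (reasonable possibility, yes or no) and seriousness as separate items.

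SAEs over 24 weeks in Cohorts A and B are part of the primary endpoint (Protocol Table 2-1; SAP 2.5). SAP 2.6.1 tabulates events by seriousness and prepares separate serious and non-serious tables for registry posting. It has no rule of its own for liver cases.

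**The concern.** A site that follows the causality paragraph to the letter would not report as serious a liver case that the closing paragraph calls serious. The case would then miss 24-hour reporting and the SAE count, although the same protocol asks for both. 6.5.3.1 itself describes a combined transaminase and bilirubin rise as possibly severe DILI, and SAP Table 5-4 lists hepatotoxicity as an event of special interest.

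There is also a structural problem. If seriousness waits on a causality rating, part of the SAE count rests on an investigator's opinion of cause in an open-label study with no data monitoring committee (Protocol 10.2.1). The 50% threshold also adds a second causality standard beside the yes/no item in 10.1.1.

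**Working it through.** **The plan's own figure.** The only number the plan derives for the primary endpoint is the sample size (Protocol 12.9, SAP 3): expected rate p = 0.18, half-width d = 0.12, two-sided 95%, normal approximation.

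- n = 1.96² × p(1 − p) / d² = 3.8415 × 0.1476 / 0.0144 = 39.37, rounded up to 40 evaluable.
- 40 / (1 − 0.10) = 44.4, rounded up to 45 enrolled.

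Both match the plan. This point does not dispute them.

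**The rules side by side.** The closing paragraph has no 'only'. It states a sufficient condition and excludes nothing, so where its condition is not met it is silent.

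| Liver case | Causality paragraph | Closing paragraph | 10.1.2 with 10.1.3 | Conflict? |
|---|---|---|---|---|
| 1. Confirmed, no alternative cause found, treatment not rated above 50% (for example, incomplete work-up) | Excluded by 'only' | SAE | Judged without regard to cause | Yes, within 6.5.3.1 |
| 2. Another cause more likely, but a 10.1.2 criterion such as hospitalization is met | Excluded on a literal reading | Silent | SAE, reportable | Yes, with 10.1.2 and 10.1.3, unless 'only' governs just the DILI label |
| 3. Another cause found, treatment still rated above 50% | SAE | Silent | Judged without regard to cause | No |
| 4. Rated probable but not confirmed on repeat testing | SAE | Silent | Judged without regard to cause | No |
| 5. Confirmed, another cause plausible, treatment rated 50% or less, no other seriousness criterion | Excluded by 'only' | Silent | Open to medical judgement | Unclear |

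The direct contradiction inside 6.5.3.1 is row 1. Row 2 is a clash with the general rules if the sentence is read as governing reporting. Row 5 turns on whether the causality paragraph is meant to displace the judgement that 10.1.2 allows; the text does not say.

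**Size.** Patients are counted once per category (SAP 2.5.1, 2.6.1), so a reclassified case changes the overall SAE rate only if that patient has no other SAE. Assuming all enrolled patients are treated and so enter the Safety Set:

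- Cohort A or B: 1/45 = 2.2 points per patient (1/40 = 2.5 points if only 40 count).
- Illustration with no other SAE in the cohort, exact 95% intervals: 0/45 = 0% (0 to 7.9%) against 1/45 = 2.2% (0.06 to 11.8%).

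The documents give no frequency for combined transaminase and bilirubin elevations, so the number of such patients cannot be estimated from them.

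**The case against.** The strongest reply is that the two paragraphs are meant to be read together. 6.5.3.1 calls DILI a diagnosis of exclusion. If work-up finds no other cause, treatment will usually outweigh the alternatives and the 50% test will be met. 'Only' may limit just the DILI label. On that reading nothing is lost, and 10.1.2 still applies to every case.

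Much of this stands.

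- A reader might infer that the rules contradict each other in both directions. They do not: the closing paragraph excludes nothing, so rows 3 and 4 are not conflicts.
- A reader might infer that a case meeting neither liver rule cannot be an SAE. The documents do not say that 6.5.3.1 overrides 10.1.2. Fatal, life-threatening, disabling or hospitalized cases qualify whatever the cause, and 10.1.2 leaves room for judgement on the rest.
- A reader might take 10.1.3 as the contradicted definition. It governs events that are already serious; the definition free of cause is in 10.1.2.
- A reader might infer that the work-up delays expedited reporting. The documents give no work-up duration, and the 24 hours run from learning of the SAE.
- Much of the signal is kept elsewhere. Laboratory grades are assigned programmatically from observed values (SAP 2.6.4). An abnormality requiring a change in study medication is still an AE (Protocol 10.1.1). Events of special interest are summarized whether serious or not (SAP 2.6.2), and AEs leading to discontinuation are tabulated separately.

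The benign reading does not remove the problem, because the sentence goes on from the label to SAE reporting. Row 1 therefore remains, and row 2 remains for anyone who takes the sentence as written.

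**Conclusion.** The inconsistency is real but narrow. Read literally, the causality paragraph excludes a confirmed unexplained case that the closing paragraph requires, and appears to exclude liver cases from another cause that 10.1.2 and 10.1.3 require. Both paragraphs tie seriousness to cause, which the general sections keep apart.

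In practice, only cases whose sole route to seriousness is the medically-significant criterion should change status. This assumes that sites apply 10.1.2 to the rest. Each such patient with no other SAE moves the rate in Cohort A or B by 2.2 points. How many there will be is unknown, probably few. Laboratory grades and the AE, special-interest and discontinuation summaries are unaffected; what changes is the SAE count and the split between serious and non-serious tables. The study is descriptive with no hypothesis test (Protocol 12.4.1), so error rates and sample size are untouched.

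One patient in Cohort C would be 1/25 = 4.0 points, but that cohort is outside the primary objective, so the figure should not be quoted against the primary endpoint.

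**What to change.** Reconcile the last two paragraphs of 6.5.3.1 with 10.1.2 and 10.1.3:

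1. Let 'only such a case' limit the DILI label, and delete the closing words of that sentence on SAE reporting.
2. State that SAE status follows 10.1.2 whatever the causality rating.
3. State that the closing paragraph is a sufficient condition for an SAE, not an exclusive one.
4. State that causality is recorded separately, as in 10.1.1, and updated as follow-up within the 10.1.3 timelines.

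Whether every case meeting the laboratory criteria should be an SAE, including those with an established other cause, and under what term, is for the sponsor to decide; reconciling the text does not require it. The change concerns reporting only, not treatment.

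The cost is a one-paragraph protocol clarification and a reminder to sites. The downside is small: a few more SAEs later recorded as unrelated. The sample size and the analysis methods stay as they are.

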6.6 Additional treatment guidance

6.6.1 Treatment compliance

Total daily dose of study treatment administered with start and end date will be collected on the Dosage Administration Record eCRF page. Name, start and end dates of any Concomitant

[REDACTED]

Medications and Surgical and Medical procedures will be collected on the Prior and Concomitant medications and Surgical and Medical procedures eCRFs respectively.

Compliance will be assessed by the investigator and/or study personnel at each patient visit and information provided by the patient and/or caregiver will be captured in the Drug Accountability Form. This information must be captured in the source document at each dispensing patient visit.

6.6.2 Emergency breaking of assigned treatment code

Not Applicable

6.6.3 Special Considerations for COVID-19 infection

All patients that who present with COVID-19 infection or who become COVID-19 positive on treatment should be placed immediately on treatment break or delay while a determination is made about the next steps

A request to start or continue treatment of COVID-19 positive patients should be considered in the context of medical necessity to start or continue treatment with the study drug.

Many patients with previous COVID-19 infection may be appropriate to be considered eligible for inclusion in the study if tested negative after initial infection

6.7 Preparation and dispensation

The investigator or responsible site personnel must instruct the patient or caregiver to take the study drugs as per protocol. Study drug(s) will be dispensed to the patient by authorized site personnel only. All dosages prescribed to the patient and all dose changes during the study must be recorded on the Dosage Administration Record eCRF.

Each study site will be supplied with study drug in packaging as described under investigational drugs section.

A unique medication number is printed on the study medication label.

The IRT will select the study treatment to dispense to the subject. The study medication has a 2-part label (base plus tear-off label), immediately before dispensing the package to the subject, site personnel will detach the outer part of the label from the package and affix it to the subject's source document.

6.7.1 Handling of study treatment and additional treatment

6.7.1.1 Handling of study treatment

Study treatment must be received by a designated person at the study site, handled and stored safely and properly and kept in a secured location to which only the investigator and designated site personnel have access. Upon receipt, all study treatment must be stored according to the instructions specified on the labels and in the Investigator's Brochure. Clinical supplies are to be dispensed only in accordance with the protocol. Technical complaints are to be reported to the respective Novartis CO Quality Assurance.

Medication labels will be in the local language and comply with the legal requirements of each country. They will include storage conditions for the study treatment but no information about the subject except for the medication number.

The investigator must maintain an accurate record of the shipment and dispensing of study treatment in a drug accountability log. Monitoring of drug accountability will be performed by monitors during site visits or remotely and at the completion of the trial. Subjects will be asked to return all unused study treatment and packaging at the end of the study or at the time of discontinuation of study treatment.

At the conclusion of the study, and as appropriate during the course of the study, the investigator will return all unused study treatment, packaging, drug labels, and a copy of the completed drug accountability log to the Novartis monitor or to the Novartis address provided in the investigator folder at each site.

6.7.1.2 Handling of additional treatment

Not Applicable

6.7.2 Instruction for prescribing and taking study treatment

See [Section 6.1.1](#)

7 Informed consent procedures

Eligible subjects may only be included in the study after providing (witnessed, where required by law or regulation), IRB/IEC-approved informed consent.

If applicable, in cases where the subject's representative(s) gives consent (if allowed according to local requirements), the subject must be informed about the study to the extent possible given his/her understanding. If the subject is capable of doing so, he/she must indicate agreement by personally signing and dating the written informed consent document.

Informed consent must be obtained before conducting any study-specific procedures (e.g. all of the procedures described in the protocol). The process of obtaining informed consent must be documented in the subject source documents.

Novartis will provide to investigators in a separate document a proposed informed consent form that complies with the ICH GCP guidelines and regulatory requirements and is considered appropriate for this study. Any changes to the proposed consent form suggested by the investigator must be agreed by Novartis before submission to the IRB/IEC.

Information about common side effects already known about the investigational drug can be found in the Investigator's Brochure (IB). This information will be included in the subject informed consent and should be discussed with the subject during the study as needed. Any new information regarding the safety profile of the investigational drug that is identified between IB updates will be communicated as appropriate, for example, via an investigator notification or an aggregate safety finding. New information might require an update to the informed consent and then must be discussed with the subject.

Women of child-bearing potential must be informed that taking the study treatment may involve unknown risks to the fetus if pregnancy were to occur during the study and agree that in order to participate in the study they must adhere to the contraception requirements.

Male subjects on asciminib treatment must be informed that if a female partner becomes pregnant while the male subject is enrolled in the study, contact with the female partner will be attempted to request her consent to collect pregnancy outcome information.

A copy of the approved version of all consent forms must be provided to Novartis/sponsor after IRB/IEC approval.

8 Visit schedule and assessments

The Assessment Schedule ([Table 8-1](#)) lists all of the assessments when they are performed. All data obtained from these assessments must be supported in the participant's source documentation.

Participants should be seen for all visits/assessments as outlined in the assessment schedule ([Table 8-1](#)) or as close to the designated day/time as possible. Missed or rescheduled visits should not lead to automatic discontinuation. Participants who prematurely discontinue the study for any reason should be scheduled for a visit as soon as possible, at which time all of the assessments listed for the final visit will be performed. At this final visit, all dispensed investigational product should be reconciled, and the adverse event and concomitant medications recorded on the CRF.

[figure not shown]
No eCRF will be used as a source document.

(S) is defined as "Source"

[figure not shown]
(D) is defined as "Data Based"

Table 8-1 Assessment schedule

[figure not shown]
| Visit name | Category | Protocol Section 8 | Screening Phase | Treatment Phase | | | | | | | | | | | | | | | |
|------------------------------------|----------|--------------------|----------------------------------|-----------------|--------------|--------|--------|---------|---------|---------|---------|---------|---------|---------|---------|---------|---------|---------|--|
| | | | | Week 1 Day 1 | Week 2 Day 1 | Week 4 | Week 8 | Week 12 | Week 16 | Week 20 | Week 24 | Week 28 | Week 32 | Week 36 | Week 40 | Week 44 | Week 48 | Week 52 | |
| Obtain Informed Consent | D | | X (Screening window -56 days) | | | | | | | | | | | | | | | | |
| Eligibility checklist/registration | D | | X | | | | | | | | | | | | | | | | |
| Cohort Assignment | D | 6.3.2 | X | | | | | | | | | | | | | | | | |
| Demography | D | 8.2 | X | | | | | | | | | | | | | | | | |
| Inclusion/exclusion criteria | D | 5.1 | X | | | | | | | | | | | | | | | | |
| Medical History | D | 8.2 | X | | | | | | | | | | | | | | | | |
| Disease History | D | 8.2 | X | | | | | | | | | | | | | | | | |
| Mutation status | D | 8.2 | X | | | | | | | | | | | | | | | | |
| Prior antineoplastic therapy | D | 8.2 | X | | | | | | | | | | | | | | | | |
| Prior TKI therapy | D | 8.2 | X | | | | | | | | | | | | | | | | |

[figure not shown]
[figure not shown]
| Visit name | Category | Protocol Section 8 | Screening Phase Screening/ Baseline (Day -21 to -1) | Treatment Phase | | | | | | | | | | | | | | | |
|--------------------------------------|----------|--------------------|---|-------------------------------------|--------------|--------|--------|---------|---------|---------|---------|---------|---------|---------|---------|---------|---------|---------|--|
| | | | | Week 1 Day 1 | Week 2 Day 1 | Week 4 | Week 8 | Week 12 | Week 16 | Week 20 | Week 24 | Week 28 | Week 32 | Week 36 | Week 40 | Week 44 | Week 48 | Week 52 | |
| Prior/concomitant medications | D | 6.2 | X | Continuous | | | | | | | | | | | | | | | |
| Physical examination | S | 8.3 | X | X | | X | X | X | X | X | X | X | X | X | X | X | X | X | |
| Extramedullary Involvement | D | 8.3 | X | X | | X | X | X | X | X | X | X | X | X | X | X | X | X | |
| ECOG Performance status | D | 8.3 | X | X | | X | X | X | X | X | X | X | X | X | X | X | X | X | |
| Height | D | 8.3 | X | | | | | | | | | | | | | | | | |
| Weight | D | 8.3 | X | X | | | | X | | | X | | | X | | | X | | |
| Vital signs | D | 8.3 | X | X | X | X | X | X | X | X | X | X | X | X | X | X | X | | |
| Laboratory assessments | | | | | | | | | | | | | | | | | | | |
| Hematology | D | 8.3.1 | X | X | X | X | X | X | X | X | X | X | X | X | X | X | X | X | |
| Chemistry | D | 8.3.1 | X | X | X | X | X | X | X | X | X | X | X | X | X | X | X | | |
| Chemistry-Hemoglobin A1c | D | 8.3.1 | X | Week 12 and as clinically indicated | | | | | | | | | | | | | | | |
| Serum Pregnancy test (if applicable) | D | | X | | | X | X | X | X | X | X | X | X | X | X | X | X | | |
| Hepatitis markers | D | | X | | | | | | | | | | | | | | | | |

| Visit name | Category | Protocol Section 8 | Screening Phase | Treatment Phase | | | | | | | | | | | | | | |
|--|----------|--------------------|-----------------|-------------------------|--------------|--------|----------------|---------|---------|---------|---------|---------|---------|---------|---------|---------|---------|---------|
| | | | | Week 1 Day 1 | Week 2 Day 1 | Week 4 | Week 8 | Week 12 | Week 16 | Week 20 | Week 24 | Week 28 | Week 32 | Week 36 | Week 40 | Week 44 | Week 48 | Week 52 |
| Liver assessments | D | | | as clinically indicated | | | | | | | | | | | | | | |
| Efficacy assessments | | | | | | | | | | | | | | | | | | |
| Blood collection for BCR-ABL1 quantification by RQ-PCR | D | 8.4.1 | X | | | X | | X | | | | X | | | X | | | X |
| | | | | | | | | | | | | | | | | | | |
| Hematologic Response Assessment | D | 8.4.1 | | | | | | X | | | X | | | X | | | | X |
| Cardiac Assessments | | | | | | | | | | | | | | | | | | |
| ECG | D | 8.3.2 | X | X | X | X | X ^a | X | | | X | | | X | | | X | |

[figure not shown]

| Visit name | Category | Protocol Section 8 | Screening Phase | Treatment Phase | | | | | | | | | | | | | | | |
|---|----------|--------------------|-----------------|-----------------|--------------|--------|--------|---------|---------|---------|---------|---------|---------|---------|---------|---------|---------|---------|--|
| | | | | Week 1 Day 1 | Week 2 Day 1 | Week 4 | Week 8 | Week 12 | Week 16 | Week 20 | Week 24 | Week 28 | Week 32 | Week 36 | Week 40 | Week 44 | Week 48 | Week 52 | |
| Cardiovascular risk factor assessments (including Family History) | D | 8.3.2 | X | | | | | | | | | | | | | | | | |
| Echocardiogram | D | 8.3.2 | X | | | | | | | X* | | | | | | | | | |
| Pulmonary Function Test | D | 8.3.2 | X* | | | | | | | X* | | | | | | | | | |
| Adverse events / SAE | D | 10.1 | X | Continuous | | | | | | | | | | | | | | | |

| | Category | Protocol Section 8 | Screening Phase | Treatment Phase | | | | | | | | | | | | | | |
|-------------------------------|----------|--------------------|--|-----------------|--------------|--------|--------|---------|---------|---------|---------|---------|---------|---------|---------|---------|---------|---------|
| Visit name | | | Screening/ Baseline (Day -21 to -1) | Week 1 Day 1 | Week 2 Day 1 | Week 4 | Week 8 | Week 12 | Week 16 | Week 20 | Week 24 | Week 28 | Week 32 | Week 36 | Week 40 | Week 44 | Week 48 | Week 52 |
| Asciminib Drug administration | D | 6.1 | | Continuous | | | | | | | | | | | | | | |
| Progression Status | D | | | | | | | X | | | X | | | | | | X | |

[figure not shown]
| | Category | Protocol Section 8 | Treatment Phase | | | | EOT /Early Discontinuation | 30 days Safety follow-up |
|-------------------------------|----------|--------------------|-----------------|---------|---------|---------|----------------------------|--------------------------|
| Visit Name | | | Week 56 | Week 60 | Week 64 | Week 68 | Week 72 | |
| Prior/concomitant medications | D | 6.2 | Continuous | | | | | |

| Visit Name | Category | Protocol Section 8 | Treatment Phase | | | | EOT /Early Discontinuation | 30 days Safety follow-up |
|--|----------|--------------------|-------------------------|----------------|---------|---------|----------------------------|--------------------------|
| | | | Week 56 | Week 60 | Week 64 | Week 68 | | |
| Physical examination | S | 8.3 | X | X | X | X | X | |
| Extramedullary Involvement | D | 8.3 | X | X | X | X | X | |
| ECOG Performance | D | 8.3 | X | X | X | X | X | |
| Weight | D | 8.3 | | X | | | X | |
| Vital signs | D | 8.3 | X | X | X | X | X | |
| Laboratory assessments | | | | | | | | |
| Hematology | D | 8.4.1 | X | X | X | X | X | |
| Chemistry | D | 8.4.1 | X | X | X | X | X | |
| Chemistry-Hemoglobin A1c | D | 8.4.1 | as clinically indicated | | | | | |
| Serum Pregnancy test (if applicable) | D | 8.3 | X | X | X | X | X | |
| Liver assessments | D | | as clinically indicated | | | | | |
| Efficacy assessments | | | | | | | | |
| Blood collection for BCR-ABL1 quantification by RQ-PCR | D | 8.4.1 | | X ^β | | | X | |

| Visit Name | Category | Protocol Section 8 | Treatment Phase | | | | EOT /Early Discontinuation | 30 days Safety follow-up |
|---|----------|------------------------|-----------------|---------|---------|---------|----------------------------|--------------------------|
| | | | Week 56 | Week 60 | Week 64 | Week 68 | | |
| | | | | | | | | |
| Hematologic Response Assessment | D | 8.4.2 | | | | | X | |
| Cardiac Assessments | | | | | | | | |
| ECG | D | 8.3.2 | | X | | | X | |
| Cardiovascular risk factor assessments (including Family History) | D | 8.3.2 | | | | | X | |
| Echocardiogram | D | 8.3.2 | | | | | X* | |
| Adverse events / SAE | D | 10.1.1 | Continuous | | | | | |
| | | | | | | | | |

| Visit Name | Category | Protocol Section 8 | Treatment Phase | | | | EOT /Early Discontinuation | 30 days Safety follow-up |
|---|----------|--------------------|-----------------|---------|---------|---------|----------------------------|--------------------------|
| | | | Week 56 | Week 60 | Week 64 | Week 68 | | |
| | | | | | | | | |
| Asciminib Drug administration | D | | Continuous | | | | | |
| Antineoplastic therapies since discontinuation of study treatment | D | | | | | | X | |
| Progression status | D | | | | | X | | |
| | | | | | | | | |

X = assessment to be recorded in the clinical database or received electronically from a vendor

S = assessment to be recorded in the source documentation only

[figure not shown]
α = only applicable to Cohort C

* = If clinically indicated

** = Upon confirmed loss of MMR and/or End of Treatment

β = only applicable if the visit is in-person

Study visits from Week 2 Day 1 will have an allowed “visit window” of +/- 2 day for Week 2 Day 1. Study visits from Week 4 to Week 72 (EOT) will have an allowed “visit window” of +/- 7 days.

